| Objectives | 
Study 1:
 
 • To investigate whether the skin autofluorescence (SAF) levels increase over time in prevalent and incident people on peritoneal dialysis (PD) and haemodialysis (HD). • To investigate one-year survival in relation to increased SAF levels. • To determine the most important factors associated with changes in SAF over time. • To investigate the association of increased SAF levels with morbidity, changes in visual function, health-related quality of life and nutritional status. 
Study 2:
 
 • To investigate whether the correction of malnutrition by an intensive nutritional intervention results in a decrease in SAF levels in people on PD and HD. |
| Trial Configuration | 
Study 1: longitudinal/prospective.
 
Study 2: observational non-randomized proof of principle study.
 |
| Setting | Outpatient secondary care setting. |
| Sample size estimate | 
Sample size Study 1: The primary outcome of the study is one-year survival in relation to increased SAF levels in people on HD and PD. With a power of 80%, a two-sided alpha of 5% and an expected hazard ratio of 3.5 and 2.0 in people on PD and HD, respectively, 100 HD and 40 PD participants will be needed.
 
Sample size Study 2: Since this is an observational proof of principle study, it would be reasonable to include 40 dialysis participants (either HD or PD).
 |
| Number of participants | 
Study 1:
 
 • 100 participants undergoing maintenance HD treatment (dialysis vintage greater than 3 months). • 40 PD dialysis participants with a dialysis vintage greater than 3 months. • 30 incident participants starting either HD or PD treatment (dialysis vintage \leq 3 months). 
Study 2: 40 malnourished participants on maintenance HD and PD.
 |
| Eligibility criteria | 
HD cohort:
 
 • Age: \geq18 years (no upper age limit). • At least three dialysis sessions per week for 3 or 4 hours. • Dialysis with biocompatible membranes. |

| | |
|------------------------------|---|
| | 
 • Able to give informed consent. 
PD cohort:
 
 • Age: ≥ 18 years (no upper age limit). • Dialysis with lactate/bicarbonate-buffered solutions with different glucose concentrations as prescribed for routine clinical care. • Able to give informed consent. |

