AGE accumulation is postulated as the one of the modulating factors that drives visual disorders (Kandarakis et al., 2014); the increased accumulation secondary to hyperglycaemia in diabetes is thought to cause vascular basement membrane thickening and destruction of pericytes from the retinal capillary bed in diabetic retinopathy (Singh et al., 2014). The accumulation of AGE has also been reported to be a mechanism in the deterioration in visual acuity associated with increasing age (Ishibashi et al., 1998). Separately, the accumulation of AGE in other metabolic diseases (e.g. end stage kidney disease [ESKD]) has been found to cause nerve and eye dysfunction. Ocular abnormalities and therefore visual disturbances are reported in people with ESKD but the mechanism for this has not been fully explored or understood. In animal studies, AGE accumulation is seen

in the lens, cornea and vitreous humour (Darlene et al., 2011). In humans, systemic AGE levels and visual acuity scoring have not been previously investigated.

Because of the adverse outcomes strongly associated with higher levels of SAF, several options focused on reducing the accumulation of AGE have been proposed. One of these promising interventions is the reduction of dietary AGE; it has been suggested that cooking techniques that avoid very high temperatures such as poaching, steaming, stewing and boiling can significantly reduce the AGE content of food when compared to frying, broiling, grilling and roasting (Uribarri et al., 2010); nevertheless, most of the evidence regarding dietary modifications to reduce exogenous AGE is of low quality and therefore further studies are required (Kellow and Savige, 2013).

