Nevertheless, analysis of baseline data from Study 1 has identified strong associations between higher SAF and malnutrition whereas no correlations were observed between higher SAF and high dietary AGE intake. Correction of malnutrition may therefore represent a more important dietary intervention to reduce accumulation of AGE in people receiving dialysis. We further reasoned that placing people with malnutrition on a restrictive diet may worsen their malnutrition and we have therefore adapted our original research plan to include an observational study to assess the impact of correcting malnutrition on SAF by providing a dietitian supervised nutritional support intervention, which essentially involves the usual/standard dietetic care/advice provided by the NHS with some additional supervision, follow-up and approved dietary supplements (also provided by the NHS), rather than a randomised trial of dietary AGE restriction.

The results from the present project will benefit people on dialysis because they may demonstrate that the correction of malnutrition decreases the SAF levels in this population. Published observational studies suggest that reduction of SAF levels will in turn be associated with a reduction in the high morbidity and mortality rates associated with chronic dialysis and, consequently, healthcare costs. Improved survival and reduced comorbidity would also be expected to improve the quality of life of people on dialysis.

TRIAL / STUDY OBJECTIVES AND PURPOSE

PURPOSE

The purpose of the present project is to investigate the association between AGE accumulation and adverse outcomes (mainly mortality) and the impact of a dietary intervention on SAF levels in people on HD and PD.

PRIMARY OBJECTIVES

Study 1:

- To investigate whether the SAF levels increase over time in prevalent and incident HD and PD participants.
- To investigate one-year survival in relation to increased SAF levels.

Study 2:

- To investigate whether the correction of malnutrition by an intensive nutritional intervention results in a decrease in SAF levels in people on PD and HD.

SECONDARY OBJECTIVES

Study 1:

- To determine the most important factors associated with change in SAF over time.
- To investigate the association of increased SAF levels with morbidity, health-related quality of life and nutritional status.
- To investigate the association between SAF levels and changes in visual function.

Study 2:

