Routine blood/laboratory tests will be performed at baseline and monthly and will include haemoglobin, HbA1C, urea, creatinine, potassium, phosphate, calcium, sodium, albumin, total proteins, cholesterol, triglycerides and intact parathyroid hormone. Pre- and post-dialysis blood samples (10 mL) will be taken at baseline, 3, 6, 9 and 12 months of follow-up and centrifuged to obtain at least 2 mL of serum and 2 mL of plasma which will be frozen and stored at -80°C for subsequent analysis of circulating AGE levels (CML and pentosidine) and markers of inflammation (TNF- α , IL-6, CRP and others).

Nutritional assessments will be performed at baseline and at 6 and 12 months of follow-up and will include: three 24-h dietary recalls to assess energy, fat and protein intake, a validated food frequency questionnaire to evaluate dietary AGE intake; the 7-point scale SGA for the classification of the nutritional status (normal, mild-moderate malnutrition and severe malnutrition) and anthropometric measurements and indexes (weight, height, mid-arm circumference, triceps skinfold thickness, body mass index, hand-grip strength and mid-arm muscle area).

Participants will have all aspects of their visual acuity assessed at baseline and 12 months. Those on HD will be tested before and after a single mid-week dialysis session. Participants will initially be asked a screening questionnaire to assess whether or not they note a change in their visual acuity or experience visual disturbances peri dialysis. The assessments will include near, distance, contrast and colour vision assessed using the Jaeger near vision chart, standardized Early Treatment Diabetic Retinopathy Study (EDTRS) testing, Pelli-Robson Contrast Sensitivity Chart, and Ishihara Color Vision Test, respectively. Participants will be asked to bring their glasses or wear their contact lenses on the study day to assess best corrected visual acuity.

Health-related quality of life will be evaluated at baseline and at 6 and 12 months of follow-up with the 36-Item Short Form Health Survey (SF-36) and EQ5D questionnaire.

After the first year of the study, SAF readings and questionnaires will be repeated once a year for up to five years.

Study 2 - Observational non-randomised proof of principle study

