To compare baseline versus final evaluations, Wilcoxon test or paired t-test will be used in the case of dimensional variables, and McNemar test in the case of categorical variables. Intergroups comparisons will be performed using Mann Whitney test or Student t test for continuous variables and χ^2 test or Fisher's exact test for categorical variables. To determine the significance and strength of associations, Pearson's correlation coefficient will be used for analyses of associations between continuous variables and Spearman rank for nonparametric variables. Linear regression analysis will be used to identify determinants of AGE accumulation. Cox proportional hazards models will be used to investigate the prognostic value of the accumulation of AGE for predicting mortality. A p-value less than or equal to 0.05 will be considered to have statistical significance.

Sample size calculation of Study 1 was performed by using the software nQuery Advisor v.6.0.

Sample size Study 1:

The primary outcome for sample size determination is one-year survival in relation to increased SAF levels in people on HD and PD. With a power of 80%, a two-sided alpha of 5% and an expected hazard ratio of 3.5 and 2.0 in people on PD and HD, respectively (based on similar findings of the studies of Kimura et al. [2014] and Siriopol et al. [2015]), 100 HD and 40 PD participants will be needed.

Sample size Study 2

Since this is a proof of principle study, it would be reasonable to include 40 dialysis participants (either HD or PD).

Assessment of efficacy

Primary endpoints

Study 1:

- Mean change in SAF levels (AU) from baseline to 12 months of follow-up.
- One-year survival.

Study 2:

Mean change in SAF levels (AU) after 6 months of a dietitian supervised intensive nutritional support intervention

Secondary endpoints

Study 1:

- Regression coefficients for identifying factors associated with the accumulation of AGE.
- Correlation coefficients for analysing the association of SAF levels with morbidity, biochemistry, circulating AGE levels, inflammatory biomarkers, visual function, health-related quality of life and nutritional status.

Study 2:

- Changes in biochemistry, circulating AGE levels, inflammatory biomarkers, visual function, health-related quality of life and nutritional status.

Assessment of safety

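### Study 1 asks how SAF relates to change in visual function, but plans only an unadjusted correlation, not stated as change, that age and diabetes alone could make significant

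*Combined protocol and SAP*

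**What the plan says.** The synopsis (Objectives, Study 1) has the aim "To investigate the association of increased SAF levels with morbidity, changes in visual function, health-related quality of life and nutritional status". The Secondary Objectives section gives vision its own line: "To investigate the association between SAF levels and changes in visual function". Both refer to change.

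The Study 1 secondary endpoints under Trial / Study Configuration list visual function among the variables to be associated with SAF levels, without mentioning change. Assessment of efficacy, Secondary endpoints, gives the analysis: "Correlation coefficients for analysing the association of SAF levels with morbidity, biochemistry, circulating AGE levels, inflammatory biomarkers, visual function". The Study 2 entry just below it does speak of changes in visual function.

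Statistics, Methods, sets out the tools:

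- Correlation: "Pearson's correlation coefficient will be used for analyses of associations between continuous variables and Spearman rank for nonparametric variables".
- Linear regression: "Linear regression analysis will be used to identify determinants of AGE accumulation".
- Cox models: "Cox proportional hazards models will be used to investigate the prognostic value of the accumulation of AGE for predicting mortality".
- Paired tests (Wilcoxon, paired t, McNemar) for baseline against final values, with no link to SAF.

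The Study 1 data collection section supplies what a change analysis needs: "Participants will have all aspects of their visual acuity assessed at baseline and 12 months". HD participants are tested before and after one mid-week session. Demographics and diabetes history are recorded at baseline, and modality defines the cohorts.

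**The concern.** There are two gaps between objective and analysis.

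First, the outcome is not pinned down. The objective is about change. The endpoint and analysis name visual function without saying whether it is a level or a change, at which visit, or (in HD) before or after dialysis. SAF is measured at baseline and 3, 6, 9 and 12 months, and the plan does not say which value enters.

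Second, nothing separates SAF from its known correlates. The background reports that SAF rises with age in both modalities and with diabetes in HD. It also refers to "the deterioration in visual acuity associated with increasing age" and to retinal damage in diabetes. Anyone older or diabetic may therefore have both higher SAF and poorer sight. The same section puts forward accumulation of advanced glycation end-products as a driver of visual disorders, so a significant coefficient is likely to be read as support for that mechanism. An unadjusted correlation cannot carry that reading.

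**Working it through.** The plan gives no sample size or power for the visual analysis, so there is no stated figure to reproduce. The Study 1 numbers were set for survival and do not bear on this point.

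**Inputs from the documents.** Prevalent participants: 100 HD + 40 PD = 140. With at most 30 incident participants: 170. Threshold: p ≤ 0.05 per test.

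**Inputs that are assumptions.** The documents give no correlation of age or diabetes with SAF or with vision. Values from 0.2 to 0.5 are used, the same for SAF and for vision, with age and diabetes independent of each other. SAF has no effect of its own.

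**Step 1: induced correlation.**

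r = r(SAF, age) × r(vision, age) + r(SAF, diabetes) × r(vision, diabetes)

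**Step 2: chance of p ≤ 0.05, by Fisher's z.**

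P = Φ(√(n − 3) · atanh r − 1.96) + Φ(−√(n − 3) · atanh r − 1.96)

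Example: r = 0.25, n = 140. atanh 0.25 = 0.2554; √137 = 11.70; product 2.99; Φ(2.99 − 1.96) = Φ(1.03) = 0.85. The second term is negligible.

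| Assumed correlations with both SAF and vision | Induced r | n = 140 | n = 170 |
|---|---|---|---|
| Age 0.2 only | 0.04 | 7.5% | 8.1% |
| Age 0.3 only | 0.09 | 18% | 21% |
| Age 0.3, diabetes 0.2 | 0.09 + 0.04 = 0.13 | 33% | 39% |
| Age 0.3, diabetes 0.3 | 0.09 + 0.09 = 0.18 | 57% | 65% |
| Age 0.4, diabetes 0.3 (or age 0.5 only) | 0.25 | 85% | 91% |

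The smallest correlation that reaches p ≤ 0.05 is 0.166 at n = 140 and 0.151 at n = 170. Over the same settings the rate is 7% to 71% for 100 participants (the HD cohort alone) and 6% to 34% for the 40 PD participants.

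**Step 3: if vision enters as change.** Simulation with 3,000 runs per setting, assuming that change in vision correlates 0.10 with age and 0.15 with diabetes, gave p ≤ 0.05 for the unadjusted correlation in about 9% to 15% of runs at n = 140 and 10% to 20% at n = 170.

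**Step 4: adjusted model.** In the same simulations, regressing 12-month vision on SAF, baseline vision, age and diabetes gave p ≤ 0.05 in 4.4% to 6.1% of runs for n = 100 to 170, close to 5%. The unadjusted level correlation gave 12% to 92%. Vision was simulated as continuous, so Step 4 does not speak for the near-vision or colour-vision scores.

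**The case against.** **The analysis line is shorthand.** Read with the objective, visual function could mean change. That is fair, and the text does not exclude it. The correlation would still be unadjusted, and the plan would still not say whether change is across a year or across a dialysis session. The larger figures in Step 2 apply only to the level-with-level reading.

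**The objective says association, and SAF is presented as a risk marker.** A correlation that runs through age is a genuine marginal association, so the rates above are not type I errors for that weaker question. This stands. They measure how often the result would mislead someone who takes it as an independent SAF effect, which the background invites.

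**The background sentence on age and acuity presents AGE accumulation as a mechanism of that decline.** So the protocol does not treat age as wholly separate from SAF. But age comes before both, and adjusting for it does not remove a step between SAF and vision.

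**Other SAF correlates are named.** Dialysis vintage and PD glucose exposure are cited for PD. The documents do not tie either to vision, so on their own evidence these are not shared causes.

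**Linear regression may not suit every test.** This stands for the Jaeger and Ishihara results, which may be ordinal or bounded, and the fix allows for it.

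A reader might also infer that the 12-month visual assessment goes unused. It does not: the paired baseline-versus-final tests can use it. They simply do not relate the change to SAF.

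**Conclusion.** The concern holds in a limited form. The objective is about change in vision. The only analysis linking SAF to vision is an unadjusted correlation that does not mention change, and no planned model adjusts vision for baseline, age or diabetes.

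A reader might go further and conclude that age and diabetes would make the correlation significant. The documents do not support that, because they give no correlation sizes. With no independent SAF effect the rate runs from about 8% to about 91% at n = 140 to 170, depending on assumed correlations, or about 9% to 20% if vision enters as change. The diabetes link with SAF is cited for HD only, and the PD cohort is small. What can be said is that shared causes could produce significance, and with moderate correlations often would.

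Nor does the mismatch extend to quality of life or nutrition, since the Secondary Objectives section asks about change only for vision. This is a secondary objective, and neither primary endpoint is affected. It is worth correcting because the correction is cheap.

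**What to change.** Bring the Study 1 endpoint and analysis wording into line with the objective, and state:

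- **Outcome:** change in each visual test from baseline to 12 months. In HD, use the pre-dialysis test at both visits and report within-session change separately.
- **Predictor:** baseline SAF.
- **Distance acuity and contrast sensitivity:** regress the 12-month value on baseline SAF, the baseline value of the same test, age, diabetes and modality. Report the SAF coefficient with its 95% confidence interval.
- **Jaeger and Ishihara:** an ordinal model or a partial Spearman correlation with the same adjustment.
- **Raw correlations:** descriptive only.

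The cost is a few sentences and a handful of models. No visit, test or participant is added. There are two downsides: participants without a 12-month visual test drop out of these models, and the adjusted SAF effect will usually be smaller than the raw correlation.

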- Does not wish to participate.
- Renal transplant.
- Pregnancy or breast feeding or intending pregnancy.
- Expected survival less than one year (for Study 1).

Expected duration of participant participation

Participants will be participating in the Study 1 for five years and in the Study 2 for 24 months.

Removal of participants from therapy or assessments/Participant Withdrawal

Participants will be withdrawn from the study if they withdraw their consent at any point, receive a renal transplant or decline to comply with the dietetic intervention (Study 2). Female participants will be withdrawn from the study if they become pregnant.

Participants may be withdrawn from the study either at their own request or at the discretion of the Investigator. The participants will be made aware that this will not affect their future care. Participants will be made aware (via the information sheet and consent form) that should they withdraw the data collected to date cannot be erased and, with their consent, may still be used in the final analysis.

If participants fail to attend for their study visits, a member of the research team will try to contact them by telephone within 24 hours of their appointment and by written correspondence within a week of the missed appointment. Multiple attempts at contact will be made by the research team over a period of a month before stating that a participant has been lost to follow-up.

With participant consent, data that is collected prior to withdrawal will be kept and analysed as part of the data set. The date, time and reason for participant withdrawal will be documented on the case report form (CRF).

To ensure attainment of adequate numbers of participants for the analysis to be valid, the research team will attempt to recruit other participants to replace any who withdraw from the study.

Informed consent

The process for obtaining participant informed consent will be in accordance with the Research Ethics Committee (REC) guidance, Good Clinical Practice (GCP) and any other regulatory requirements that might be introduced.

The research team have both training and experience in assessing participant capacity and gaining informed consent in the clinical context.

Detailed information will be provided on the study to ensure that participants understand the purpose and potential risks involved. The study will not involve participants who are unable to represent their own interests or are particularly susceptible to coercion.

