Once participants have given their informed consent, relevant participant characteristics will be extracted from electronic data captured in medical records and from a self-report questionnaire at baseline and will include demographic characteristics, educational level, occupation status, family history, duration of renal replacement therapy, dialysis adequacy, aetiology of CKD, medical history (e.g. history of cardiovascular disease, diabetes and hypertension), current co-morbidities, alcohol history, smoking status and current medication. For the PD participants, information regarding the type of PD and the volume of the different PD solutions will also be recorded.

The accumulation of AGE will be assessed by measuring SAF using a validated Autofluorescence Reader (AGE Reader, DiagnOptics, Groningen, The Netherlands) at baseline, 3, 6, 9 and 12 months of follow-up. The method has been previously described by Meerwaldt et al. (2005). As described in the study by Siriopol et al. (2015), "the autofluorescence reader illuminates a skin surface of 1 cm², guarded against surrounding light, with an excitation light source between 300 and 420 nm (peak excitation ≈370 nm). Light from the skin is measured with a spectrometer (AVS-USB2000, Avantes Inc., Eerbeek, The Netherlands) in the 300-600 nm range, using a 200-µm glass fibre". SAF will be measured as the ratio between emission and excitation, calculated in arbitrary units (AU), by

Page 16 of 30

Skin autofluorescence as a risk marker in people receiving dialysis
Protocol draft 4.5 Final Version 2.0 04.10.2017

This protocol is confidential and the property of the University of Nottingham. No part of it may be transmitted, reproduced, published, or used by others persons without prior written authorisation from the University of Nottingham

dividing the intensity of the fluorescent light coming from the skin (measured as area under the curve [AUC] of fluorescent wave lengths between 420 and 600 nm) by the intensity of the emitted light (measured as AUC of wave lengths between 300 and 420 nm) multiplied by 100. For each participant, three measurements will be performed on the volar surface of the lower arm at \approx 10 cm below the elbow, ensuring that the area has normal skin without visible vessels, scars or other abnormalities. For HD participants, only the non-fistula arm will be used and readings will be undertaken within the first hour of HD treatment (Siriopol et al., 2015).

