Tolerability and safety of the nutritional support intervention during the proof of principle study (Study 2) will be assessed by direct interview. If any serious adverse event (SAE) is reported during the study, it will be recorded on an appropriate SAE report form.

Procedures for missing, unused and spurious data

All SAF measurements, biochemistry, nutritional and quality of life assessments for Study 1 and 2 will be used in the statistical analysis, including data from participants who did not complete the entire study protocol.

Definition of populations analysed

Study 1:

Full Analysis set: All participants included in the protocol for whom at least one post-baseline assessment of the primary endpoint is available.

Per protocol set: All participants in the Full Analysis set who are deemed to have no major protocol violations that could interfere with the objectives of the study.

Study 2:

Full Analysis set: All randomised participants, who participated in at least one treatment and for whom at least one post-baseline assessment of the primary endpoint is available.

Per protocol set: All participants in the Full Analysis set who are deemed to have no major protocol violations that could interfere with the objectives of the study.

ADVERSE EVENTS

The occurrence of an adverse event as a result of participation within this study is not expected and as such no adverse event data will be collected.

ETHICAL AND REGULATORY ASPECTS

ETHICS COMMITTEE AND REGULATORY APPROVALS

The study will not be initiated before the protocol, informed consent forms and participant information sheets have received approval / favourable opinion from the REC, and the respective NHS Research & Development (R&D) department. Should a protocol amendment be made that requires REC approval, the changes in the protocol will not be instituted until the amendment and revised informed consent forms and participant information sheets (if appropriate) have been reviewed and received approval / favourable opinion from the REC and R&D departments. A protocol amendment intended to eliminate an apparent immediate hazard to participants may be implemented immediately providing that the REC are notified as soon as possible and an approval is requested. Minor protocol amendments only for logistical or administrative changes may be implemented immediately; and the REC will be informed.

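### Study 1 classes an incomplete study day as a withdrawal, against its own withdrawal criteria, so later SAF readings and possibly deaths can go unobserved; the Full Analysis set also needs its endpoint named

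*Combined protocol and SAP*

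**What the plan says.** **Incomplete study days.** The Compliance section says that Study 1 needs no assessment of compliance. It then classes a participant who does not complete the study day as withdrawn, and refers to the participant withdrawal section.

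**Withdrawal.** That subject is covered under Stopping rules and discontinuation, and again under Removal of participants from therapy or assessments. Between them the grounds are withdrawn consent or own request, pregnancy, renal transplant, refusal of the Study 2 dietetic intervention, and investigator discretion. An incomplete day is not listed. Both sections speak of retaining, with permission, data gathered up to withdrawal, and the second says that replacements will be sought. For a visit not attended at all, both prescribe telephone and written contact, with attempts over a month before loss to follow-up is declared.

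**Schedule.** SAF is read "at baseline, 3, 6, 9 and 12 months of follow-up", then yearly for up to five years.

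**Endpoints and sets.** Study 1 has two primary endpoints: "Mean change in SAF levels (AU) from baseline to 12 months of follow-up", and one-year survival. Its Full Analysis set is "All participants included in the protocol for whom at least one post-baseline assessment of the primary endpoint is available"; the Per protocol set is nested inside it. The Cox sentence under Statistics, Methods names no set. The missing-data paragraph keeps SAF, biochemistry, nutritional and quality-of-life data, "including data from participants who did not complete the entire study protocol"; it does not mention survival.

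**The concern.** A participant who cannot finish a dialysis-day assessment is treated more severely than one who does not come at all. The first is withdrawn at once; the second is pursued for a month. Frailer patients are the likelier ones to leave a long day of blood sampling, vision testing, dietary recall and questionnaires unfinished. If withdrawal ends follow-up, their later SAF readings are lost and their survival time is censored for a reason related to prognosis. That touches both primary endpoints: SAF change loses readings and perhaps representativeness, and one-year survival may look better than it is.

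The analysis-set wording raises a related question. If its post-baseline condition meant SAF and the set were also used for survival, anyone who died before the month 3 reading would be left out, and the outcome itself would decide entry to the analysis.

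**Working it through.** **Setting the passages side by side**

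| Event at a Study 1 visit | Section | Consequence |
|---|---|---|
| Visit not attended | Both withdrawal sections | Contact attempts over a month, then lost to follow-up |
| Visit started, not finished | Compliance | Withdrawal |
| Listed grounds for withdrawal | Both withdrawal sections | Withdrawal; earlier data kept with permission; replacement sought |

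The second row has no counterpart among the listed grounds. The missing-data paragraph does not repair this: it uses readings that exist and cannot supply those never taken.

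**Possible size of the withdrawal effect (illustration).** The documents give neither mortality nor the frequency of incomplete days. Assumed: 15% true one-year mortality; a sicker 20% with 3 or 4 times the death rate of the rest; constant hazards; incomplete days at months 3, 6 and 9; all observation ending at withdrawal.

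The hazard λ of the healthier group solves 0.8·exp(−λ) + 0.2·exp(−kλ) = 0.85. For k = 3, λ = 0.1192, and the sicker hazard is 3 × 0.1192 = 0.358. In each quarter, each group's share under observation is multiplied by exp(−hazard/4), then by 1 minus its incomplete-day rate. The large-sample Kaplan-Meier estimate is the product of the quarterly survival proportions. For k = 3 with rates of 10% and 2%: 0.9594 × 0.9607 × 0.9618 × 0.9628 = 0.8535, a mortality of 14.65%.

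| Sicker hazard | Incomplete per visit, sicker v others | Withdrawn before month 12 | Deaths unobserved | Kaplan-Meier mortality |
|---|---|---|---|---|
| ×3 | 10% v 2% | 9.0% | 6.9% | 14.65% |
| ×3 | 15% v 3% | 13.1% | 10.2% | 14.48% |
| ×4 | 20% v 3% | 14.7% | 13.4% | 14.06% |
| ×3 | 5% v 5% | 13.2% | 6.9% | 15.0% |

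The last row is a check. With incomplete days unrelated to prognosis, 6.9% of deaths still go unobserved but the bias is zero. The share of unobserved deaths therefore measures lost information, not bias. The bias in the other rows is 15 − 14.65 = 0.35 to 15 − 14.06 = 0.94 percentage points. For comparison, the binomial standard error at 15% is √(0.15 × 0.85/100) = 3.6 points for 100 HD participants and √(0.15 × 0.85/40) = 5.6 points for 40 PD participants.

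Precision, first and third rows:
- Log hazard ratio: the standard error rises by 1/√(1 − 0.069) = 1.04 to 1/√(1 − 0.134) = 1.07.
- SAF change: of those alive at month 12, 90.6% and 85.1% remain under observation, so its standard error rises by about 1/√0.906 = 1.05 to 1/√0.851 = 1.08.

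**The analysis-set question.** Take the SAF reading and apply it to survival. With one-year survival S, Weibull shape k and f = 0.25^k, the share of first-year deaths falling before month 3 is (1 − S^f)/(1 − S), and the mortality seen is 1 − S^(1−f).
- Constant hazard (k = 1), S = 0.85: (1 − 0.9602)/0.15 = 26.5% of deaths; mortality reads 1 − 0.85^0.75 = 11.5%; standard error × 1/√(1 − 0.265) = 1.17.
- Lower early risk (k = 1.5, f = 0.125), plausible because people expected to live less than a year are excluded: (1 − 0.9799)/0.15 = 13.4%; mortality reads 13.3%; standard error × 1.07.
- Over assumed mortality of 10 to 25%, the share is 26.0 to 27.8% for k = 1 and 13.1 to 14.1% for k = 1.5.

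The hazard ratio for baseline SAF is essentially unaffected. People who die before month 3 are in no later risk set, so omitting them only drops the early event terms. A simulation (60 runs of 10,000, constant hazard, 15% mortality, equal SAF split) gave 2.01 with everyone and 2.01 without early deaths for a true ratio of 2.0, and 3.49 against 3.47 for 3.5.

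**The case against.** **On incomplete days.** The Compliance sentence points back to the withdrawal section, where an incomplete day is not a criterion, so a sensible team might never withdraw anyone on this ground. Investigator discretion could equally cover such a case. A reader might infer that the study has no means of tracing deaths after withdrawal. The documents do not support that: under Case Report Forms, a recruitment log with names and hospital or NHS numbers is kept for all enrolled participants, with follow-up as one of its purposes. It does not mention withdrawal or vital status, so the means exist but no instruction to use them does. Replacement looks largely moot: recruitment was due to end in August 2017 and this version is dated 04.10.2017. Every rate in the illustration is assumed, and the bias is well inside sampling error. All of this limits the size; none of it removes the contradiction.

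**On the analysis set.** A reader might infer that the plan drops early deaths from the survival analysis. No passage says so. A recorded death is itself a post-baseline assessment of survival, and the synopsis states: "The primary outcome of the study is one-year survival in relation to increased SAF levels in people on HD and PD". The Statistics section is narrower ("The primary outcome for sample size determination is one-year survival in relation to increased SAF levels in people on HD and PD"), so it favours the survival reading without settling it. The matching Study 2 set, "All randomised participants, who participated in at least one treatment and for whom at least one post-baseline assessment of the primary endpoint is available", concerns SAF, but it speaks of randomisation in a non-randomised study and looks like template text, so it is weak evidence for the SAF reading. Most analysts would supply the right set unprompted.

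**Conclusion.** The contradiction over incomplete study days is on the page and should be removed. Followed literally, the Compliance rule ends later SAF readings, and possibly observation of death, after one unfinished day, probably more often in sicker participants. The size cannot be known from the documents. Under the assumptions shown, bias in one-year mortality is under one percentage point, and standard errors rise by about 4 to 8%. It would be zero if follow-up in fact continues after an unfinished day.

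The unnamed endpoint in the Full Analysis set is a minor clarification. On the natural reading nothing is lost. Only if the set were read as SAF-based and used for survival would about 13 to 28% of first-year deaths drop out (assumed mortality 10 to 25%). Absolute survival would then be overstated and precision reduced, with the baseline-SAF hazard ratio essentially unbiased.

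**What to change.** 1. **Compliance section.** Reconcile it with the two withdrawal sections: an incomplete study day is missing data for that visit, not a ground for withdrawal or replacement. Later visits go on as scheduled, and vital status is followed where consent allows, using the identifiers in the recruitment log.
2. **Definition of populations analysed, Study 1.** State that the post-baseline condition applies to the SAF-change analysis only. State that one-year survival, and any Cox model using baseline SAF, includes all consented participants with a baseline SAF, timed from baseline to death or censoring.
3. **Cox covariate.** The Methods text says only that AGE accumulation is the predictor. Say whether this is baseline SAF or change in SAF. If it is change, a landmark start is needed instead, and deaths before the landmark are then outside the analysis by design.

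**Cost.** A short amendment to two sections and one sentence under Methods, with no new type of measurement. Following vital status after a true withdrawal may need amended consent or ethics committee review, and anyone already withdrawn for an incomplete day may need to be re-contacted.
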